## Evaluation of Best Overall Response

The best overall response is the best response recorded from the start of the treatment until disease progression/recurrence (taking as reference for PD the smallest measurements recorded since the treatment started). In general, the patient's best response assignment will depend on the achievement of both measurement and confirmation criteria.

**Table 9: Best Overall Response Evaluation**

Best Overall Response Evaluation		
Target Lesion	New Lesion	Overall Response
CR	No	CR
PR	No	PR
SD	No	SD
PD	Yes or No	PD

Patients with a global deterioration of health status requiring discontinuation of treatment without objective evidence of disease progression at that time should be classified as having “symptomatic deterioration”. Every effort should be made to document the objective progression even after discontinuation of treatment.

In some circumstances it may be difficult to distinguish residual disease from normal tissue.

When the evaluation of complete response depends on this determination, it is recommended that the residual lesion be investigated (fine needle aspirate/biopsy) to confirm the complete response status.

## Immune Related Response Criteria

A growing body of literature indicates that radiographic responses to immunotherapy may have different patterns and kinetics than what would be expected with traditional cytotoxic therapies. To account for these differences we will also characterize radiographic outcomes using the immune related response criteria outlined by Wolchok and colleagues [57]. See Appendix 6. This criteria will be used to measure the abscopal response rate and DCR (CR+PR+SD) and determine whether the study should proceed to stage 2 and is worthy of further study during the Simon two-stage study.

## **Confirmation**

The main goal of confirmation of objective response is to avoid overestimating the response rate observed. For reporting the study outcomes the response rate and confirmed response rate will be made clear. For interval evaluation of response rates during the Simon-two stage study responses do not need to be confirmed for the study to progress. To be assigned the status of confirmed responses must be confirmed by repeat assessments that should be performed no less than 4 weeks after the criteria for response are first met. Longer intervals as determined by the study protocol may also be appropriate. In the case of SD, follow-up measurements must have met the SD criteria at least once after study entry at a minimum interval (in general, not less than 6-8 weeks) that is defined in the study protocol. For PD all results should be confirmed as described in section 8.2.

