### 8.2 Discontinuation Due to Disease Progression

Immunotherapeutic agents such as epacadostat and SD-101 may produce antitumor effects by potentiating endogenous cancer-specific immune responses. The response patterns seen with such an approach may extend beyond the typical time course of responses seen with cytotoxic agents and can manifest as a clinical response after an initial increase in tumor burden or even the appearance of new lesions.

Immune related RECIST will be used for assessment of tumor response for the purposes of managing subjects on Protocol treatment and decision making for discontinuation of study therapy due to disease progression. PD should be confirmed no earlier than 4 weeks later according to the criteria outlined in Table 8. Subjects who are deemed clinically unstable or who have biopsy proven new metastatic lesions are not required to have repeat imaging for confirmation. This decision will be based on clinical judgment of a subject's overall clinical condition, including performance status, clinical symptoms, and laboratory data. At a minimum, subjects must meet the following criteria for continued treatment on study after disease progression is identified at a tumor assessment:

When feasible, subjects should not be discontinued until progression is confirmed; however, the decision to continue study treatment after the first evidence of disease progression is at the investigator's discretion based on the clinical status of the subject.

Subjects may receive study treatment while waiting for confirmation of PD if they are clinically stable as defined by the following criteria:

- No decline in ECOG performance status.
- Absence of new or worsening symptoms.
- Absence of rapid progression of disease.
- Absence of progressive tumor at critical anatomical sites (e.g., spinal cord compression) requiring urgent alternative medical intervention.

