## **Duration of Overall Response**

The duration of overall response is measured from the time measurement criteria are met for CR or PR (whichever status is recorded first) until the first date that recurrence or PD is objectively documented, taking as reference for PD the smallest measurements recorded since the treatment started.

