**Progression-Free Survival (PFS)**

PFS is defined as the duration of time from start of treatment to time of progression or death, whichever occurs first.

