## **12.4 Efficacy**

As a secondary endpoint, all responses will be reported using irRECIST and RECIST 1.1 definitions [56]. Because of the potential heterogeneity of the patients, all results will be considered preliminary and hypothesis generating for future studies. Response rate will be summarized by exact binomial confidence intervals. Disease free survival will be summarized with Kaplan-Meier plots to describe the outcome of patients treated on this protocol. The median DFS time will be estimated using standard life table methods.

If a patient is enrolled on the study and is subsequently removed from treatment for any reason prior to the first CT/MRI scan they are not evaluable for treatment efficacy, that patient will not be included in analysis of treatment efficacy specific to response criteria, but will still be included in the general safety analysis with all other patients. Patients who are not evaluable for treatment efficacy will be replaced by additional patient enrollment to ensure a full cohort of evaluable patients.

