## 17.6 Appendix 6: Immune-Related Response Criteria

Increasing clinical experience indicates that traditional response criteria (e.g., Response Evaluation Criteria in Solid Tumors, Version 1.1 [RECIST v1.1] and World Health Organization [WHO]) may not be sufficient to characterize fully activity in the new era of target therapies and/or biologics. In studies with cytokines, cancer vaccines, and monoclonal antibodies, complete response, partial response, or stable disease has been shown to occur after an increase in tumor burden as characterized by progressive disease by traditional response criteria. Therefore, conventional response criteria may not adequately assess the activity of immunotherapeutic agents because progressive disease (by initial radiographic evaluation) does not necessarily reflect therapeutic failure. Long-term effect on the target disease must also be captured. The immune-related response criteria (irRC) are criteria that attempt to do that by enhancing characterization of new response patterns that have been observed with immunotherapeutic agents (i.e., ipilimumab) [57]. (Note: The irRC only index and measurable new lesions are taken into account.)

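### Section 10.1 requires every progression to be confirmed under the irRECIST rule of section 8.2, with no exemption for the parallel RECIST 1.1 analysis, and the PFS definition names no scan date

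*Combined protocol and SAP*

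**What the plan says.** The plan uses two sets of response criteria in parallel. Objective 1.3.1, note d of the Study Calendar (section 9.1) and Table 10 call for ORR and PFS under both RECIST 1.1 and irRECIST. Section 12.4 adds that "all responses will be reported using irRECIST and RECIST 1.1 definitions".

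The RECIST-type criteria in section 10.1 (Response Criteria) define PD as a 20% increase in the sum of longest diameters or any new lesion. Table 9 carries PD straight through to the overall response. Neither mentions a second scan. Best overall response is counted up to progression.

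The Confirmation subsection of section 10.1 then ends: "For PD all results should be confirmed as described in section 8.2". Section 8.2 gives its own scope: "Immune related RECIST will be used for assessment of tumor response for the purposes of managing subjects on Protocol treatment and decision making". Its rule is "PD should be confirmed no earlier than 4 weeks later according to the criteria outlined in Table 8", with an exemption: "Subjects who are deemed clinically unstable or who have biopsy proven new metastatic lesions are not required to have repeat imaging for confirmation".

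Two definitions in section 10.1 bear on the date. Duration of response runs "until the first date that recurrence or PD is objectively documented". For PFS the text is "PFS is defined as the duration of time from start of treatment to time of progression or death, whichever occurs first", with no mention of a first or a confirming scan.

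**The concern.** A confirmation rule written for irRECIST and for treatment decisions is applied to all PD results, and so to the RECIST 1.1 analysis as well. Appendix 6 gives the reason for having immune criteria at all: under conventional criteria, "progressive disease (by initial radiographic evaluation) does not necessarily reflect therapeutic failure". The immune criteria are there to pick up patients who respond after an apparent progression. If RECIST 1.1 PD must also be confirmed, some of those patients move into the RECIST 1.1 figures too.

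There are two consequences. First, an unconfirmed first PD stops being a RECIST 1.1 PFS event and no longer closes the window for best response, so a later PR or CR can count in RECIST 1.1 ORR. Second, because the PFS definition names no scan, two analysts could date the same confirmed event at least four weeks apart.

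**Working it through.** **1. The plan's own figures.** The only stated operating characteristics are those of the two Simon designs in section 12.1: 80% power at one-sided 0.05 against a DCR of 5%. The probability of a positive result is the sum, over first-stage counts x > r1, of P(X1 = x) × P(X2 ≥ r + 1 − x).

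| Cohort | X1, X2 | Rule | Alpha (p = 0.05) | Power |
|---|---|---|---|---|
| Solid tumour | Bin(16, p), Bin(14, p) | x ≥ 2, total ≥ 4 | 0.0478 | 0.8067 at p = 0.20 |
| Lymphoma | Bin(7, p), Bin(7, p) | x ≥ 1, total ≥ 3 | 0.0274 | 0.8101 at p = 0.30 |

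The stated power is reproduced. Section 10.1 (Immune Related Response Criteria) bases this decision on the immune-related criteria, so nothing here depends on how RECIST 1.1 PD is handled. No sample size or power is stated for RECIST 1.1 ORR or PFS.

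**2. One hypothetical patient under both readings.** The sum of diameters is 100 at baseline, 125 at Day 60 (+25%) and 65 at Day 120 (−35%).
- Printed criteria and Table 9, with no confirmation: best response PD, PFS 60 days.
- With the Confirmation sentence applied: the Day 60 PD is not confirmed, best response can be PR, and PFS runs past Day 120.

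Section 8.2 also brings in Table 8, whose footnote judges the repeat scan against the first-PD scan. The PR definition in section 10.1 uses the pre-treatment baseline, so the cross-reference adds a second reference point.

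**3. PFS if confirmed PD is dated at the first scan.** Only unconfirmed PDs matter. The documents give no rate for these, so the following are assumptions: exponential time to progression with median m of 60 to 180 days; scans every 60 days as in the Study Calendar; a share u of first PDs unconfirmed (5% or 10%); and the clock restarting at that scan with the same median.

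Let q = 2^(−60/m), the chance of passing one 60-day interval. Without confirmation, P(PFS > 120) = q². For a patient whose first PD is set aside, it is 1 − (1 − q)² = 2q − q². The shift is therefore u × [(2q − q²) − q²] = u × 2q(1 − q).

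| m (days) | q | q² | Shift, u = 5% | Shift, u = 10% |
|---|---|---|---|---|
| 60 | 0.500 | 0.250 | 0.025 | 0.050 |
| 90 | 0.630 | 0.397 | 0.023 | 0.047 |
| 120 | 0.707 | 0.500 | 0.021 | 0.041 |
| 180 | 0.794 | 0.630 | 0.016 | 0.033 |

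This is about 2 to 5 percentage points. Simulation under the same assumptions agrees.

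**4. PFS if confirmed PD is dated at the confirming scan.** Each such event moves by at least 4 × 7 = 28 days, or by 60 days if the next scan on the calendar is used. With u = 0, any patient whose first PD is after Day 60 now has PFS beyond 120 days, so the share becomes q: 0.50 to 0.79, against 0.25 to 0.63 with first-scan dating.

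**5. ORR.** No rate can be derived from the documents. Each patient reclassified from PD to responder moves ORR by 1/30 = 3.3 points in a full solid tumour cohort, or 1/14 = 7.1 points in a full lymphoma cohort.

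**The case against.** The strongest reply is that the sentence can be read narrowly. It follows the immune-related paragraph and points to a section whose stated scope is irRECIST. The printed RECIST-type criteria are silent on confirmation rather than expressly against it, and the best-response paragraph says that assignment generally depends on confirmation as well as measurement. The sentence says should, and section 8.2 exempts some patients from repeat imaging. The Appendix 6 remark is background, not an operating rule.

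Much of this limits the point but does not remove it. The Confirmation subsection has its own general heading and refers to all PD results. Its stated aim is to avoid overestimating the response rate, which confirming CR and PR serves; confirming PD can only leave that rate the same or raise it. Appendix 6 already contains the confirmation rule for irPD, so an irRECIST-only sentence would add little. The argument here rests on the criteria as printed, not on any outside statement of RECIST 1.1.

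Four stronger readings are tempting, and the documents do not support them.
- **That confirmation contradicts dating PD at first documentation.** Whether an event counts and when it is dated are separate questions. Appendix 6 itself counts the confirmation interval from first documentation, and the first-documentation wording in section 10.1 covers duration of response only.
- **That the two sets of criteria become one.** Section 10.1 uses summed longest diameters with 30% and 20% thresholds, and any new lesion is PD. Appendix 6 uses products of diameters with 50% and 25% thresholds and adds measurable new lesions to the burden. These differences remain.
- **That a comparison planned in objective 1.3.1 is lost.** The objective asks for preliminary data under both criteria and states no comparison.
- **That median RECIST 1.1 PFS would be 47% to 100% longer.** That follows from 88/60 = 1.47 and 120/60 = 2.00 if 1 − (0.20 × 30 + 0.30 × 14)/44 = 77% of patients progress at Day 60. It uses irRECIST DCR thresholds as RECIST PD rates, counts early deaths and unassessable patients as PD, ignores the exemptions in section 8.2, and assumes confirming-scan dating, which no section states.

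**Conclusion.** The concern holds as a minor defect of definition. The Confirmation sentence extends an irRECIST treatment-management step to a parallel RECIST 1.1 analysis whose printed criteria have no such step, and the PFS event date is left open.

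The size depends on a choice the plan does not make. With first-scan dating, the effect on the share with PFS beyond 120 days is about 2 to 5 points, given the assumed 5% to 10% unconfirmed and assumed medians of 60 to 180 days. With confirming-scan dating, each such event is at least 28 days later. The ORR effect is indirect and cannot be sized from the documents.

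Only exploratory endpoints are affected. The stage 2 decision and the Simon power and alpha stand.

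**What to change.** In section 10.1 (Confirmation), replace the last sentence with wording such as: *Progression by irRECIST is confirmed as set out in section 8.2 and, once confirmed, is dated at the scan that first showed it. For analysis, progression by RECIST 1.1 is taken, without confirmation, at the first scan meeting the PD criteria under Response Criteria; RECIST 1.1 best response and PFS end at that date.* State the same event dates, by criterion, in the PFS definition.

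This concerns analysis only. Decisions on continuing treatment under section 8.2 are not altered, and no extra scans or patients are needed. It should be settled before the data are analysed. The cost is that RECIST 1.1 ORR and PFS may look slightly less favourable.

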## **Duration of Overall Response**

The duration of overall response is measured from the time measurement criteria are met for CR or PR (whichever status is recorded first) until the first date that recurrence or PD is objectively documented, taking as reference for PD the smallest measurements recorded since the treatment started.

## **Duration of Stable Disease**

SD is measured from the start of the treatment until the criteria for disease progression are met, taking as reference the smallest measurements recorded since the treatment started.

The clinical relevance of the duration of SD varies for different tumor types and grades, but in general, if two consecutive CT/MRI scans show stable disease, or the patient experiences four months of stable disease, then we will consider this to be stable disease

Therefore, it is highly recommended that the protocol specify the minimal time interval required between two measurements for determination of SD. This time interval should take into account the expected clinical benefit that such a status may bring to the population under study.

## **Treatment Tolerability**

Treatment tolerability will be measured as the percentage of patients who remain free of treatment intolerance as defined in section 6.6.

## **Abscopal Response Rate (ARR)**

ARR is defined as the percentage of patients that achieve an objective tumor response at unirradiated lesions as defined by irRECIST criteria

**Objective Response Rate**

ORR is defined as the percentage of patients that achieve PR or CR.

**Disease Control Rate (DCR)**

DCR is defined as the percentage of patients that achieve an objective tumor response or have stable disease to therapy as best response and is defined as complete response (CR) + partial response (PR) + stable disease (SD). This endpoint has been shown to be more meaningful, and translating to survival advantage, in a number of tumor immunotherapy studies.

**Progression-Free Survival (PFS)**

PFS is defined as the duration of time from start of treatment to time of progression or death, whichever occurs first.

**Overall Survival (OS)**

OS is defined as the duration of time from the start of treatment to death from any cause.

**Reporting of Results**

All patients included in the study must be assessed for response to treatment, even if there are major protocol treatment deviations or if they are ineligible. Each patient will be assigned one of the following categories: 1) complete response, 2) partial response, 3) stable disease, 4) progressive disease, 5) early death from malignant disease, 6) early death from toxicity, 7) early death because of other cause, or 8) unknown (not assessable, insufficient data).

All of the patients who met the eligibility criteria should be included in the main analysis of the response rate. Patients in response categories 4-8 should be considered as failing to respond to treatment (disease progression). Thus, an incorrect treatment schedule or drug administration, or failure to complete all prescribed study therapy, does not result in exclusion from the analysis of the response rate. Sub-analyses may then be performed on the basis of a subset of patients, excluding those for whom major protocol deviations have been identified (e.g., early death due to other reasons, early discontinuation of treatment, major protocol violations, etc.). The reasons for excluding patients from the analysis should be clearly reported. There will be a planned analysis of patients who are evaluable for response (see section 12.4) which will be used for the Simon two-stage design.

The 95% confidence intervals should be provided.

**10.2 Safety**

Safety assessments will consist of monitoring and recording all adverse events, including serious adverse events, the monitoring of hematology, blood chemistry, coagulation parameters, urinalysis and the regular monitoring of vital signs, and physical condition as shown in corresponding tables. For details on AE collection and reporting, refer to the Safety section in the protocol.

**10.3 All Study Variables**

The panel of study endpoints and how they will be measured are described in Table 10.

**Table 10: Study Variables**

Endpoint	Variable	Measurement	Comment
Primary- Phase 1	MTD	CTCAE V4.03	Outlined in section 3. The maximum dose at which <2 of 6 patients experienced a DLT
Primary- Phase 1	DLT	CTCAE V4.03	Outlined in section 3. A DLT is defined as $\geq$ grade 4 injection site reaction OR $\geq$ grade 3 treatment-related non-hematologic toxicity (excluding injection site reactions) OR ORAST/ALT > 3 x ULN with bilirubin > 2 X ULN, OR pneumonitis that requires holding treatment > 14 days. Grade 3 rash will not be included as a DLT if there is no desquamation, no mucosal involvement, if it resolves without systemic corticosteroids by the next scheduled dose of epacadostat or 14 days, whichever is longer, and epacadostat dose intensity is maintained at 75% of planned dose during DLT period (i.e < 8 days of dose interruption). If epacadostat dose intensity cannot be maintained at 75% of planned dose during DLT period as a result of toxicity of any grade this will also be deemed a dose limiting toxicity.
Primary- Phase 2	Safety	CTCAE V4.03	
Primary-Phase 2	DCR (CR+PR+SD)	irRECIST	DCR is the endpoint for the Simon two-stage phase 2 study
Secondary- Phase 2	ARR	irRECIST	Objective response at unirradiated sites, the endpoint for measuring responses
Secondary- Phase 2	Treatment tolerability	CTCAE V4.03	Outlined in section 6.6. DLTs and any other treatment related adverse event requiring discontinuation of ERS therapy will be deemed treatment intolerability. Patients unable to resume epacadostat after 30 days due to toxicity will be labelled as having treatment intolerability. If more than two consecutive doses of SD-101 are missed due to toxicity the patient will be labeled as having treatment intolerability. Patients unable to receive at least 50% of the prescribed radiotherapy dose due to treatment

			toxicity will be labeled as having treatment intolerability.
Correlative	ORR	RECIST and irRECIST	
Correlative	PFS	RECIST and irRECIST	
Correlative	OS	RECIST and irRECIST	
Correlative	PBMC Immunophenotype	FACS	Blood
Correlative	PBMC gene expression	qPCR / Nanostring	Blood
Correlative	Systemic Cytokine Signature	Luminex	Serum
Correlative	Try/Kyn ratio	Mass spectrometry	Serum
Correlative	Tissue Immune Markers	IHC / IF	Tissue
Correlative	Tumor gene expression	qPCR / Nanostring	Tissue
Correlative	Mutational load	Whole exome sequencing/ RNA sequencing	Blood and Tissue
Correlative	T cell receptor diversity	TCR deep sequencing	Blood and Tissue
Correlative	Stool Microbiome	16s rRNA	Stool

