**Table 5: Dose Modifications of Epacadostat**

Dose level 1	Dose Level -1	Dose Level -2	Dose Level -3
300 mg BID	200 mg BID	100 mg BID	50 mg BID

If necessary, doses of SD-101 can be delayed up to 5 days, but must be given within the intended treatment week. If this is not possible, the dose will be skipped completely. Every attempt should be made to deliver at least 3 doses during the treatment period. If a dose is delayed, the following dose should be delivered during the next treatment week, a minimum of 5 days after the previously given dose. Subsequent doses in subsequent weeks should also be administered a minimum of 5 days after the previous dose. The dose may not be modified. If more than two consecutive doses are missed due to toxicity, the patient may continue ERS therapy, but will be labeled as having treatment intolerability.

The prescribed dose of radiotherapy can be reduced to no lower than 60% of the dose as specified per fraction in response to treatment related toxicity at the treatment lesion or prior to the onset of treatment to respect normal tissue tolerances as deemed necessary by the treating radiation oncologist. If a dose of radiotherapy is missed it can be administered later within the first week of therapy. Any radiotherapy fractions not delivered during the first week of therapy cannot be made up and those doses will be skipped. Patients unable to receive at least 60% of the prescribed radiotherapy dose due to treatment toxicity may continue ERS therapy but will be labeled as having treatment intolerance.

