### 6.7 Treatment Tolerability

DLTs and any other treatment related adverse event requiring discontinuation of ERS therapy will be deemed treatment intolerance. Patients unable to resume epacadostat after 30 days due to toxicity will discontinue ERS therapy and will be labeled as having treatment intolerance. If more than two consecutive doses of SD-101 are missed due to toxicity the patient may continue ERS therapy but will be labeled as having treatment intolerance. Patients unable to receive at least 60% of the prescribed radiotherapy dose due to treatment toxicity may continue ERS therapy but will be labeled as having treatment intolerance. Epacadostat dose reductions will not be labeled as treatment intolerance but will be reported separately.

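### Table 10 puts the radiotherapy cut-off for treatment intolerance at 50% of the prescribed dose; section 6.6, which it cites, and section 6.7 put it at 60%

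*Combined protocol and SAP*

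**What the plan says.** Section 3 makes treatment tolerability a secondary endpoint. Section 10.1 measures it as the proportion of patients without treatment intolerance. Both refer to section 6.6 for the definition.

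Section 10.3 gives Table 10 an operative role: "The panel of study endpoints and how they will be measured are described in Table 10". The tolerability row opens "Outlined in section 6.6. DLTs and any other treatment related adverse event requiring discontinuation of ERS therapy will be deemed treatment intolerability". Its radiotherapy criterion is "Patients unable to receive at least 50% of the prescribed radiotherapy dose due to treatment" toxicity; such patients are labelled intolerant.

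Section 6.6, in the radiotherapy paragraph after Table 5, has a different number: "Patients unable to receive at least 60% of the prescribed radiotherapy dose due to treatment toxicity may continue ERS therapy", but with the label of intolerance. Section 6.7, which is titled Treatment Tolerability, repeats that sentence with the same 60%.

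Two dosing rules in section 6.6 determine which delivered doses are possible. On reductions: "The prescribed dose of radiotherapy can be reduced to no lower than 60% of the dose as specified per fraction". On missed treatments: "Any radiotherapy fractions not delivered during the first week of therapy cannot be made up and those doses will be skipped".

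**The concern.** One endpoint has two cut-offs in current text, and the laxer one sits in the table that is meant to say how the endpoint is measured. An analyst who programs from the Table 10 row would count as tolerant some patients whom sections 6.6 and 6.7 count as intolerant. If the conflict is noticed only once data are in hand, the choice between the two could be made knowing its effect on the result.

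The cross-references add to this. Section 3, section 10.1 and Table 10 all cite section 6.6 alone, but the definition is split between two sections:

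- Section 6.7 adds that DLTs count as intolerance, which Table 10 also says. It is also the only place with the rule "Epacadostat dose reductions will not be labeled as treatment intolerance but will be reported separately".
- Section 6.6 is the only place that says explicitly that needing less than 50 mg BID of epacadostat is intolerability.

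**Working it through.** There is no sample-size or power figure to reproduce. The check is whether the disputed band, 50% to just under 60%, can occur, and what one patient in it does to the reported rate.

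**Inputs.** Regimens (sections 3 and 5.3.1): 8 Gy x 3 = 24 Gy, 4 Gy x 5 = 20 Gy, and 2 Gy x 2 = 4 Gy (cohort 2 only). Each fraction can be reduced to 60% of its dose, and fractions missed in week 1 are lost (section 6.6). Maximum cohort sizes (section 12.1): 30 solid tumor, 14 lymphoma.

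**Step 1: deliverable dose.** With k of n fractions given, each at 60% to 100% of nominal, the delivered share of the full regimen runs from 0.6k/n to k/n.

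- All fractions at the floor: 14.4/24 = 12/20 = 2.4/4 = 60.0%. Reduction alone never enters the band; at least one whole fraction must be lost.
- 2 Gy x 2: k=1 gives 30% to 50%. One full fraction gives 2/4 = 50.0%, which is in the band.
- 8 Gy x 3: k=1 gives 20% to 33.3% (outside). k=2 gives 40% to 66.7%, in the band when the delivered fractions average 6.0 to <7.2 Gy. Example: (8 + 4.8)/24 = 12.8/24 = 53.3%.
- 4 Gy x 5: k=1 and k=2 give at most 40% (outside). k=3 gives 36% to 60%, in the band at an average of 3.33 to <4.0 Gy. k=4 gives 48% to 80%, in the band at 2.5 to <3.0 Gy. Example: (4 + 4 + 2.4)/20 = 10.4/20 = 52.0%.

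**Step 2: the denominator.** Step 1 divides by the full nominal regimen. Section 6.6 speaks of reducing the prescribed dose itself, so the reduced prescription could be the denominator. The first example then becomes 12.8/(8 + 4.8 + 4.8) = 12.8/17.6 = 72.7%, and the second 10.4/(4 + 4 + 2.4 + 2.4 + 2.4) = 10.4/15.2 = 68.4%. Both leave the band. The 2 Gy x 2 case stays at 50% if the second fraction is lost without being re-prescribed, or if both fractions were reduced equally beforehand.

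**Step 3: overlap with DLTs.** Radiotherapy falls in week 1, inside the 30-day DLT period. Most treatment-related non-hematologic toxicity of grade 3 or higher is then a DLT (section 3), and so intolerance under both texts. The cut-off matters only for toxicity that costs radiotherapy without being a DLT: non-hematologic toxicity of grade 2 or lower, hematologic toxicity, the exempted grade 3 rash, or an injection-site reaction below grade 4.

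**Step 4: size.** Each patient in the band moves the rate by 1/n. The documents give no expected count, so 0, 1 and 2 are assumptions.

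| Patients in band | n=14 | n=30 |
|---|---|---|
| 0 | 0 | 0 |
| 1 | 1/14 = 7.1 points | 1/30 = 3.3 points |
| 2 | 2/14 = 14.3 points | 2/30 = 6.7 points |

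Illustration with one such patient and no other intolerance (exact 95% CI):

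- n=14: 100% (76.8 to 100) under Table 10, against 92.9% (66.1 to 99.8) under sections 6.6 and 6.7.
- n=30: 100% (88.4 to 100), against 96.7% (82.8 to 99.9).

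Pooled over both cohorts (30 + 14 = 44), one patient is 1/44 = 2.3 points.

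**The case against.** The strongest reply is that the protocol largely settles the matter itself. Section 3, section 10.1 and the Table 10 row all defer to section 6.6, which says 60%, and section 6.7 agrees. An analyst who follows the pointer gets 60%. That stands as to the intended value, and it makes this a slip in the table rather than a dispute between two analyses. It does not make the row correct: section 10.3 presents Table 10 as the account of how endpoints are measured, and its figure is wrong against both sections.

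A reader might infer that a grade 3 injection-site reaction gives a ready route into the band, because SD-101 is injected into the lesion before radiotherapy on day 1 and section 6.6 permits reduction "in response to treatment related toxicity at the treatment lesion". The documents do not support that much. The specific adverse-event management table recommends only acetaminophen for grades 1 to 3 and lists holding treatment at grade 4, which is a DLT. Reduction alone also cannot reach the band (step 1). Because that table is discretionary, the route is possible but weak.

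The denominator point also stands: the 8 Gy x 3 and 4 Gy x 5 examples hold only on the full-nominal reading. So does the point about population size. The plan does not say which patients form the tolerability denominator, and a larger one than 14 or 30 would shrink each shift.

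**Conclusion.** The discrepancy is real. Table 10 carries a wrong threshold for a declared secondary endpoint, and a patient at 50% to <60% because of toxicity, with no other intolerance criterion, gets opposite labels. The documents never say in words that 60% is intended, but both defining sections state it, and it matches the per-fraction reduction floor. Nothing outside the Table 10 row supports 50%.

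The consequence is small. The simplest case is confined to one optional regimen in cohort 2, and section 6.5 anticipates little toxicity from these palliative doses. The sizes rest on assumed counts of affected patients and on n=14 or n=30 as denominators.

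A reader might infer that the conflict reaches the dose decision or the efficacy conclusion. It does not: the MTD depends on DLTs, and the Simon rules use disease control rate. Nor does the cross-reference problem leave the endpoint undefined, since section 6.6 already holds the 30-day epacadostat, SD-101 and radiotherapy criteria; it is incomplete, not empty.

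**What to change.** In the treatment tolerability row of Table 10, change 50% to 60%.

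In section 3, section 10.1 and Table 10, cite sections 6.6 and 6.7 together. Citing 6.7 alone would drop the explicit rule on reductions below 50 mg BID; citing 6.6 alone omits the statements on DLTs and on epacadostat dose reductions.

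The cost is one number and three section references, best changed before the endpoint is analysed. No patients, visits or procedures are added.
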